3.2.1.2.5. PSA level

The PSA level (ng/ml) at each visit (except at Visit 2 (Baseline, Day 1 Month 0) where PSA level is not required) will be described using descriptive quantitative statistics.

PSA level will be described both in its continuous format and in categories (≤ 0.2 ng/ml; >0.2 ng/ml - <4 ng/ml; ≥ 4 ng/ml - <10 ng/ml; ≥ 10 ng/ml)

The percentage change from baseline (defined as the screening values) will be also presented.

In addition, a shift table of the change in categories between baseline and each visit will be presented.

At baseline the last test available before first injection of treatment will be used. Otherwise, in case of several samples (with a result) in the same time windows (excluding the confirmation samples), the value of the last sample will be used.

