1.2.1.1. Inclusion criteria

Each patient must meet the following criteria:

- Provide written informed consent by the patient prior to any study-related procedure
- Men aged ≥ 18 years
- Histo-pathologically confirmed adenocarcinoma of the prostate
- Radical Prostatectomy with curative intent performed no more than 8 weeks before randomisation
- High-risk criteria of disease progression, defined as follows:
 - Gleason score ≥ 8 on prostatectomy specimen, and/or
 - Pre-RP PSA level ≥ 20 ng/mL, and/or
 - Primary tumour stage 3a (pT3a) (with any PSA and any Gleason score)
- Post-RP PSA levels ≤ 0.2 ng/mL at 6 weeks.
- Eastern cooperative oncology group (ECOG)/world health organisation (WHO) performance status of 0 to 1

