1.3.2.1. Efficacy assessments

PSA

Blood samples for PSA testing will be taken every 3 months (except at Visit 2 (Baseline, Day 1 Month 0) where PSA level is not required).

Biochemical Relapse

Biochemical Relapse definition: increased PSA >0.2 ng/mL confirmed by a second measurement performed 4 to 6 weeks later. The time-point at which the first elevated PSA measurement is >0.2 ng/mL is recorded will be deemed to be the time of BR.

To note, for the identification of BR; all PSA samples will be taken into account, even if several samples are within the same time windows.

Clinical disease progression

Clinical disease progression is defined as evidence of local/locoregional recurrence and/or lymph node involvement and/or distant metastases documented by relevant standard investigations (such as ultrasound (US) guided biopsy, X-ray, computed tomography (CT) scan, or magnetic resonance imaging (MRI) guided biopsy).

Survival status

Survival status will be recorded at each visit.

Serum Testosterone

Serum testosterone in the triptorelin treatment group will be recorded at baseline, 3, 6 and 9 months. It will be assessed both as a continuous and as a qualitative variable (< 50 ng/dL / ≥ 50 ng/dL).

Health-Related Quality of Life

Health-Related Quality of Life (HRQoL) will be assessed using the FACT-P questionnaire, version 4, and the 36-item short form (SF-36) health survey, version 2 in both treatment arms at Baseline, 9, 24, and 36 months..

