Compliance

Time between first drug administration and RP (weeks) will be derived as $(\text{Date of first drug administration} - \text{Date of radical prostatectomy} + 1) / 7$.

Time between each drug intake (weeks) will be derived as $(\text{Date of drug intake at Visit } t - \text{Date of drug intake at visit } t-1 + 1) / 7$.

Partial dates of treatment will be imputed to calculate times:

- If the day is missing and month is present the 15 of the month will be used.
- If year is present and day and month are missing then the difference between years will be used.

Changes from baseline

Changes from baseline will be calculated as a difference from baseline (e.g. assessment at the visit – assessment at baseline).

Length of patient exposure in the study

Length of patient exposure in the study (months) will be calculated as [(Date of last visit attended – informed consent date) + 1] / 30.4375.

Duration of study drug exposure

Duration of study drug exposure (months) will be calculated as [(Date of last drug administration – Date of first drug administration) / 30.4375] + 3.

Adverse event

Time to onset of AE (days) = AE start date – date of randomisation.

Duration of AE (days) = (AE resolution date – AE start date) + 1.

Time-to-event criteria

BRFS (months) will be derived as (Date of first BR – date of randomisation + 1) / 30.4375.

EFS (months) will be derived as (Date of clinical disease progression or death from any cause – date of randomisation + 1) / 30.4375.

OS (months) will be derived as (Date of death from any cause – date of randomisation + 1) / 30.4375.

Disease specific mortality will be derived as (Date of death related to prostate cancer – date of randomisation + 1) / 30.4375.

PSADT (months) will be derived as (Date of sample when the first PSA value > than twice that of the first increased value – Date of sample of the first PSA value increased value (i.e. > 0.2 ng/mL) + 1) / 30.4375.

All of these time-to-event variables will be rounded to 1 decimal.

For BRFS, EFS, OS and Disease specific mortality, if the date of event or censor is prior to the date of randomisation, the data of event or censor taken into account will be the date of randomisation.

Rules for time-to-event data

The following table defines the rules for censoring data (for Kaplan-Meier analysis)

- BRFS

Event	Decision	Date of event or censor to consider for analysis
BR	Not censored	Date of BR (i.e. date of the first elevated PSA measurement is >0.2 ng/mL*)

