Month 21 [V9] ^(b)	--	--	626 to 654	596 to 686
Month 24 [V10] ^(b)	--	--	718 to 746	687 to 777
Month 27 [V11] ^(b)	--	--	809 to 837	778 to 868
Month 30 [V12] ^(b)	--	--	900 to 928	869 to 960
Month 33 [V13] ^(b)	--	--	991 to 1019	961 to 1051
Month 36 [V14] ^(b)	--	--	1083 to 1111	1052 to 1142

Time interval (days): Date of assessment – Date of baseline visit +1
 (a) serum testosterone assessment
 (b) PSA Level assessment

3.2.13. *Rules and data formats*

Data will be presented using an appropriate number of decimal places (i.e. the number of decimal places used does not imply undue precision). Raw data will be presented to the number of decimal places collected, and derived data will be presented to an appropriate number of decimal places. The appropriate number of decimal places will be determined by general practice, mathematical rationale or scientific rationale (e.g. age should be presented in whole numbers).

For summary statistics, the following will be presented: n, arithmetic mean, standard deviation, median, first quartile, third quartile, minimum and maximum.

Mean, median, quartiles and standard deviation values will be reported to one decimal place greater than the raw/derived data that they summarise. Minimum and maximum values will be reported with the same precision as the raw data.

Percentages will be reported to one decimal place and 0% will not be presented. Percentages will be calculated using a denominator of all patients in a specified population with non-missing observations. The denominator will be specified in a footnote to the tables for clarification if necessary.

P-values will be reported to three decimal places (e.g.: $p=0.037$), after rounding. P-values which are less than 0.001 will be presented as '<0.001'.

All values below or above a limit of detection (e.g. <0.1 or >100) will be listed as such. In summaries of data values below limit of detection will be set to the limit of detection. Values above limit of detection will be set to limit of detection.

All text fields must be left justified and numeric or numeric with some text specification (e.g.: not done, unknown, <4.5, ...) must be decimal justified. Dates and times will be presented in the format as defined in the data-base, i.e. [ddmmmyyyy] and [hh:mm] respectively.

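### PSA percentage change is taken from a screening value capped at 0.2 ng/mL, with undetectable results set to the assay limit, so the size of its mean and confidence interval cannot be interpreted

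*SAP*

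**What the plan says.** PSA level at each visit is a listed secondary endpoint (SAP section 3.1.2). Section 3.2.1.2.5 describes it as a continuous variable and in four categories, the lowest being 0.2 ng/mL or less. It then adds: "The percentage change from baseline (defined as the screening values) will be also presented". It also says that "a shift table of the change in categories between baseline and each visit will be presented".

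Three other provisions determine what that percentage will be:

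- **The baseline value is low by design.** Section 1.2.1.1 requires "Post-RP PSA levels ≤ 0.2 ng/mL at 6 weeks". PSA is then sampled every three months, "except at Visit 2 (Baseline, Day 1 Month 0) where PSA level is not required" (section 1.3.2.1), so screening is the only scheduled PSA before treatment. If there are several, "At baseline the last test available before first injection of treatment will be used" (section 3.2.1.2.5).
- **Undetectable results are substituted.** Section 3.2.13 states: "In summaries of data values below limit of detection will be set to the limit of detection". The only limits mentioned are general examples: "All values below or above a limit of detection (e.g. <0.1 or >100) will be listed as such". No detection limit is given for PSA.
- **The summary includes a mean and its CI.** Section 3.1.5 prescribes, for quantitative variables, the mean, SD and 95% CI of the mean, along with the median, quartiles and range.

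Section 3.2.10 defines change only as an absolute quantity: "Changes from baseline will be calculated as a difference from baseline". It has no formula for percentage change and no rule for a baseline that was not measurable.

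**The concern.** A percentage change needs a denominator that is measured and reasonably far from zero. After a successful prostatectomy neither can be relied on. Every eligible man starts between 0 and 0.2 ng/mL, and an unknown share will be below the assay limit. For those men the denominator is the limit itself.

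Two consequences follow. A man undetectable at both visits shows exactly 0%. A man who becomes detectable shows a percentage whose size depends on how low the assay can read. Averaging the zeros with a few very large values gives a mean and CI that look like an effect size on a secondary endpoint, but whose magnitude depends on a laboratory property that the SAP does not state.

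**Working it through.** The plan gives no figure for this quantity, so there is none to reproduce. The check applies the SAP's own rules.

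**Inputs from the SAP:** baseline is the screening value (3.2.1.2.5); the baseline ceiling is 0.2 ng/mL (1.2.1.1); values below the limit are set to the limit (3.2.13).

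**Assumed:** the PSA detection limit L, taken from 0.01 to 0.2 ng/mL for single patients, and a follow-up value of 0.3 ng/mL, just above the relapse threshold of 0.2 ng/mL.

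**Formula:** percentage change = 100 × (F − B) / B, where B and F are the baseline and follow-up values, each raised to L if below it.

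**1. Undetectable at screening, 0.3 ng/mL at follow-up.** Here B = L.

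| Assumed limit L (ng/mL) | Percentage change | Absolute change (ng/mL) |
|---|---|---|
| 0.2 | 100 × 0.10/0.2 = +50% | 0.10 |
| 0.1 | 100 × 0.20/0.1 = +200% | 0.20 |
| 0.05 | 100 × 0.25/0.05 = +500% | 0.25 |
| 0.01 | 100 × 0.29/0.01 = +2900% | 0.29 |

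Over this range the percentage varies by a factor of 2900/50 = 58 and the absolute change by 0.29/0.10 = 2.9. The true baseline lies between 0 and L, so the absolute change is wrong by at most L. The percentage change has no such bound, because the true baseline may be close to zero.

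**2. Undetectable at both visits.** B = F = L, so the result is 0% for any L.

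**3. Measurable baseline.** The denominator is now a real PSA value, but a small one. A rise to 0.3 ng/mL gives +2900% from 0.01, +200% from 0.1 and +50% from 0.2. All three men are eligible and all three end at the same PSA.

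**4. Arm means.** Suppose that all men are undetectable at screening, that 20% of one arm and 40% of the other reach 0.3 ng/mL, and that the rest stay undetectable.

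- L = 0.1: 0.2 × 200% = 40% and 0.4 × 200% = 80%, a difference of 40 percentage points.
- L = 0.01: 0.2 × 2900% = 580% and 0.4 × 2900% = 1160%, a difference of 580 percentage points.

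The ratio between arms is 1:2 in both cases; only the size moves. The median is 0% in both arms at either limit, because fewer than half of each arm became detectable.

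**5. Mixed baselines.** An illustrative simulation used lognormal baselines truncated at 0.2 ng/mL, with 30% of men rising to between 0.21 and 1.0 ng/mL and the rest about stable.

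| Baseline median before truncation (ng/mL) | Limit (ng/mL) | Undetectable at baseline | Mean % change | Mean PSA level (ng/mL) |
|---|---|---|---|---|
| about 0.01 | 0.003 | 16% | 2523% | 0.196 |
| about 0.01 | 0.01 | 50% | 1323% | 0.198 |
| about 0.01 | 0.1 | 98% | 151% | 0.253 |
| about 0.06 | 0.003 | under 1% | 373% | 0.231 |
| about 0.06 | 0.01 | 1% | 370% | 0.231 |
| about 0.06 | 0.1 | 80% | 145% | 0.258 |

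Where many baselines are undetectable, the limit drives the mean percentage change while the mean level moves little. Where nearly all baselines are measurable (the fourth and fifth rows), the limit hardly matters.

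**The case against.** The strongest reply is that a reader might infer that the whole PSA summary reflects the detection limit rather than PSA, and that the SAP does not establish this. It gives neither the PSA limit nor the share of men undetectable at screening. With a sensitive assay and mostly measurable baselines the limit has almost no effect (373% against 370% above). That stands. What remains in that case is the instability of a ratio on baselines of 0.2 ng/mL or less.

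Other stronger readings also fail:

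- **Non-comparable sites.** A reader might suppose that centres use assays with different limits. The SAP does not say whether PSA is tested centrally or locally, and such arrangements are commonly left to the protocol.
- **A biased comparison.** In the worked example the arms stay at 1:2 whatever the limit. With one common limit and undetectable baselines, both arms are rescaled alike. The fault shown is arbitrary size, not a biased contrast.
- **A damaged endpoint.** The listed endpoint is PSA level, which is also shown as absolute values and categories. Medians and quartiles are planned, and results below the limit are listed as recorded. BRFS and PSADT rest on absolute PSA values above 0.2 ng/mL.
- **A faulty shift table.** Eligible men do all fall in the lowest baseline category, so the table largely repeats the category table. That redundancy is harmless, and the table would reveal any randomised man whose baseline exceeded 0.2 ng/mL.

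Section 3.1.5 also says that quantitative variables will be analysed by ANOVA or ANCOVA, which could be read as extending to this percentage. Section 3.2.1.2.5 plans description only, so formal testing of it is not established.

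**Conclusion.** The concern holds in a limited form. For every man undetectable at screening, the SAP's rules make the assay limit the denominator of the PSA percentage change. For eligible men with a measurable baseline, the denominator is real but small, and the ratio is unstable and skewed. Either way, the planned mean and 95% CI cannot be read as the size of an effect. For a man undetectable at screening whose PSA rises to 0.3 ng/mL, the figure is +200% at a limit of 0.1 ng/mL and +2900% at 0.01 ng/mL.

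This rests on the entry ceiling and the substitution rule, both in the SAP, and on the screening sample being the six-week eligibility sample or close to it. The SAP does not say the last outright, but the timing makes it likely: screening at Day −14 and surgery at most eight weeks before randomisation. The detection limits and baseline distributions are assumptions, so how far the limit dominates the overall mean is unknown.

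The point concerns one descriptive summary of a secondary endpoint. It does not touch the primary analysis, and it does not show that the comparison between arms is biased.

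**What to change.** In section 3.2.1.2.5, replace the percentage change with absolute change from screening in ng/mL, which is also the only change that section 3.2.10 defines. Summarise it mainly by median and quartiles. Add the number and percentage of men below the detection limit by arm and visit, and state the limit in the table. Keep the continuous levels, the categories and the shift table as planned.

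Absolute change still uses the substituted value for undetectable results, but the resulting error for any man is no larger than the limit, and the added count shows how many men it affects.

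The cost is a small change to SAP wording and table shells, and the loss of a relative-change figure. No data collection and no primary analysis is affected.

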3.2.1.2.6. Serum testosterone

The proportion of castrated (serum testosterone < 50 ng/dL) patients at baseline and 3, 6 and 9 months post-RP will be provided for the triptorelin treatment group. Shift tables between two consecutive visits and between baseline and end of study will be presented of the number and percentage of patients castrated or not.

FACT-P measurements	SF-36v2 measurements

 • Subscales: 
 ○ Physical well-being ○ Social well-being ○ Emotional well-being ○ Functional well-being • Dimensions: 
 ○ General well-being ○ Prostate-specific concerns • Total FACT-P score 	
 • Health Domain Scales: 
 ○ Physical functioning (Raw) ○ Role-Physical (Raw) ○ Bodily Pain (Raw) ○ General Health (Raw) ○ Social Functioning (Raw) ○ Mental Health (Raw) ○ Role-Emotional (Raw) ○ Vitality (Raw) ○ Physical functioning (Norm-based) ○ Role-Physical (Norm-based) ○ Bodily Pain (Norm-based) ○ General Health (Norm-based) ○ Social Functioning (Norm-based) ○ Mental Health (Norm-based) ○ Role-Emotional (Norm-based) ○ Vitality (Norm-based) • Component Summary measures calculated from a combination of norm-based scales scores: 
 ○ Physical Component Summary ○ Mental Component Summary

These HRQoL measurements at baseline and at 9, 24 and 36 months post-RP, will be described using descriptive quantitative statistics for each treatment group (cf. Section 3.2.10 for derived FACT-P and SF-36v2). In addition the change from baseline will also be presented for each of these HRQoL measurements.

For each HRQoL measurement (subscales, dimensions, scales, component summary measures), changes will be analysed using a repeated-measures analysis of covariance using a mixed linear model with patient as a random effect, baseline, group, visit (Month 9, Month 24 and Month 36) and the interaction between group and visit as fixed effects. Correlation structures (auto-regressive (AR(1)), compound symmetry (CS) and unstructured (UN)) will be tested and the best one will be considered for the model (the model with the smaller AIC will be chosen):

Change = baseline + group + visit + group*visit + e

With:

- baseline, group, visit and group*visit as fixed effects,
- e: error $\sim N(0, \sigma e^2)$.

The syntax with SAS using the MIXED procedure will be:

```
CCI [REDACTED]
```

3.2.1.3. *Exploratory efficacy analysis*

To identify prognostic factors among Gleason score on prostatectomy specimen ($\leq 6 / = 7 / \geq 8$, with ≤ 6 considered as the reference), country, Pre-RP PSA level ($<20 / \geq 20$ ng/mL), primary tumour stage (T1 / T2 / T3 / T4 with T3 considered as the reference) and age (<65 years / ≥ 65 years) are associated with BRFS outcome, Cox proportional hazard regression models will be used. Each parameter will be analysed in an univariate model where the hypothesis of proportional risks will be checked graphically. Significant parameters at a 20%-level will be retained for the multivariate Cox model. Associations between significant parameters will be tested in order to keep only non correlated variables in the multivariate model. The association between two categorical or binary variables will be tested using Chi-square or Fisher's exact test. Associations will be considered as statistically significant if $p < 0.01$. A backward selection method will be used to identify the final set of prognostic factors (exit p-value set to be 0.05). Treatment will then be added to this final model to assess the effect of treatment when adjusted for these factors.

The syntax with SAS using the PHREG procedure will be:

```
CCI [REDACTED]
```

CCI [REDACTED]

3.2.2. *Safety*

Safety analysis will be analysed on safety population according to the actual treatment approach followed.

3.2.2.1. *Adverse events*

Adverse events will be graded by the investigator according to the NCI CTCAE version 4.0.

AEs will be coded according to the Medical Dictionary for Regulatory Activities (MedDRA; version 16.0) and will be classified by PT and SOC.

Listings will be presented for all patients (description, time to onset, duration, seriousness, grade, relationship to study drug, action taken and outcome) and sorted by treatment group, patient id, start time of AEs, primary system organ class, preferred term and verbatim text for all adverse events recorded during the study.

Listings of serious adverse events (SAE), adverse events leading to study withdrawal, leading to study drug discontinuation, drug related adverse events, adverse events with NCI CTC Grade > 2 and listings of deaths will also be presented.

Treatment Emergent Adverse Events (TEAE) will be flagged (*) in the adverse events listing and will be summarised.

For the triptorelin treatment group, a TEAE is defined as any AE that occurs during the active phase of the study if:

- it occurred up to 12 months after the first injection,
and
- it was not present prior to receiving the first dose of study drug, or
- it was present prior to receiving the first dose of study drug but the intensity increased during the active phase of the study, or
- it was present prior to receiving the first dose of study drug, the intensity is the same but the drug relationship became related during the active phase of the study.

Summary tables of adverse events will be provided with the number and percentage of patients with adverse events classified by primary system organ class, preferred term (ordered alphabetically) and associated NCI/CTC worst grade. In the event of multiple occurrences of the same adverse events being reported by the same patient, the maximum intensity (Grade 5 > Grade 4 > Grade 3 > Grade 2 > Grade 1 > missing > not applicable) and the most serious causality (related) will be chosen.

A summary table of all adverse events will be presented by treatment arm up to visit 6. An overall summary table of all adverse events will be presented starting at visit 6.

For the first year (visit 6 excluded), summary tables of adverse events will be presented separately for each treatment arm:

- For the triptorelin treatment group, treatment emergent adverse events per decreasing frequency, treatment emergent serious adverse events, treatment emergent non serious adverse events, treatment emergent drug related adverse events, treatment emergent drug related serious adverse events, treatment emergent drug related non serious adverse events, treatment emergent adverse events leading to study withdrawal and treatment emergent adverse events leading to study drug discontinuation (drug withdrawn or drug interrupted).
- For the active surveillance group, adverse events per decreasing frequency, serious adverse events, non serious adverse events and adverse events leading to study withdrawal will be presented.

For AEs starting from visit 6, the summary tables of adverse events will be presented overall. The following summary tables will be presented: adverse events per decreasing frequency, serious adverse events, non serious adverse events and adverse events leading to study withdrawal.

3.2.2.2. *Laboratory data*

A separate listing of normal ranges for SI units will be provided by age where relevant.

Laboratory data (haematology, biochemistry) will be listed in SI units and abnormal values will be flagged (High [H], Low [L], clinically significant [C], NCI-CTC grade (G)) where applicable. Any unscheduled laboratory assessments will be flagged [U] in the listings.

For haematology and biochemistry parameters the baseline will be defined as the screening values.

Summary statistics (mean, median, SD and range as appropriate) by treatment group and overall will be presented for clinical laboratory tests at each assessment (screening and 9 month) with change from baseline.

Shift tables will be presented of the number and percentage of patients with below, within or above normal range. For laboratory data, abnormal values will be flagged in the data listings and a list of clinically significant abnormal values will be presented.

In case of available retest sample, values of retest sample will be used instead of the first sample, except at baseline where the last test available before first injection of treatment will be used.

3.2.2.3. *Vital signs*

Descriptive summary statistics will be provided on safety population according to the actual treatment approach followed for vital signs. It includes assessments as detailed in the Section 1.3.2.3 'Vital signs'.

3.2.3. *Missing data and outliers*

3.2.3.1. *Missing data*

Missing data will not be imputed and dropouts will not be replaced.

Rules for missing data imputation for HRQoL will be addressed in 3.2.10 Derived Data.

3.2.3.2. *Missing or incomplete dates*

In all listings, missing or incomplete dates should be left as they have been recorded. However, for calculation / sorting / assignation based on dates, the following methods will be used:

- The most conservative approach will be systematically considered (i.e. if the onset date concomitant medication is missing / incomplete, it is assumed to have occurred during the study treatment phase except if the partial onset date or other data [stop date, ...] indicates differently).
- A missing/incomplete date of medical history or disease diagnosis will be assumed to have occurred before the study inclusion.
- If a partial date and the associated information do not allow to state about the assignation to a group / category, all the possible groups / categories will be considered (i.e.: a medication with partial start and stop dates could be considered as prior and concomitant treatment).
- Where this is possible, the derivations based on a partial date will be presented as superior inequalities (i.e. for a medication started in FEB2004 after the administration performed on 31JAN2004, the days since last dose will be " ≥ 2 ", similarly the duration of ongoing medication will be " $\geq xx$ " according to the start and last visit dates).

3.2.3.3. *Outliers*

Any outlier identified prior to data base lock which is impossible/improbable will be excluded from the analysis.

For other identified outliers, the impact should be assessed by performing the statistical analysis with the actual values and at least one other analysis eliminating or reducing the outlier effect.

If any outliers are identified after the database lock, the statistical analysis should be performed with the actual values and at least one other analysis eliminating or reducing the outlier effect.

A search of outliers for the PSA result will be performed before the database lock and actions with the sponsor will be defined during data review meeting.

3.2.4. *Patient disposition*

A summary table will present the number and percentages of patients enrolled included in each analysis set by treatment group and overall, by country and centre. The reason for patients' exclusion from each of the analysis set will also be tabulated.

The numbers of patients who were randomised, discontinued and completed the study will be tabulated by treatment group and overall. A patient is considered as having completed the study when "Completed the study" is ticked in the CRF at visit 14 (Month 36) or at one of the follow-up visit. The primary reason for early withdrawal will be provided (adverse event, protocol violation, consent withdrawn, lost-to follow-up, other) by treatment group and overall.

A summary table (and a flow chart) will be performed for each analysis set (Safety population, ITT and PP population) presenting the number and proportion of patients by treatment group and overall at each visit.

A summary table will present the duration of study drug exposure and the extent of patient exposure in the study (months). The length of exposure is defined as the number of days between the date of consent and the last study visit date.

A listing of dates of visit and calculated time interval since baseline visit (days) will be presented by patient.

3.2.5. *Withdrawals from study*

Discontinued patients will be listed and a summary table of the number and percentage of patients who withdrew from the study and the reasons for withdrawal will be presented overall and by treatment group.

3.2.6. *Demographic and baseline characteristics*

Descriptive summary statistics will be provided by treatment group and overall on the ITT population and on the safety population if there is at least 10 % difference between the safety and the ITT population, for demographic and baseline characteristics. It includes assessments as detailed in the Section 1.3.2.3 ('Demography and characteristics at baseline', 'Prostate cancer history', 'Radical prostatectomy procedure' and 'WHO/ECOG Performance Status Scale'). To assess homogeneity of treatment groups at baseline, 95% CI of proportion for qualitative variable or 95% CI of mean for quantitative variable will be provided.

In addition the proportion of patients with a Gleason score ≥ 8 on prostatectomy specimen and with a Pre-RP PSA level ≥ 20 ng/mL; with a Gleason score ≥ 8 on prostatectomy specimen and with a primary tumour stage 3a; with a Pre-RP PSA level ≥ 20 ng/mL and with a primary tumour stage 3a; with a Gleason score ≥ 8 on prostatectomy specimen and with a Pre-RP PSA level ≥ 20 ng/mL and with a primary tumour stage 3a will be tabulated.

3.2.7. *Medical and surgical history*

Descriptive summary statistics will be provided by treatment group and overall on the ITT population for ‘Significant Medical or Surgical History’.

A frequency table of the number and percentage of patients will be provided for medical history by SOC and PT.

3.2.8. *Compliance*

Descriptive summary statistics will be provided by treatment group and overall on the ITT population, for current prostate cancer therapy. It includes assessments as detailed in the Section 1.3.2.5 ‘Compliance’ and the time between first drug administration and RP (days) and the time between each drug intake (days). .

If the drug intake occurs outside the allowed time-window (time between each drug intake should be between 84 and 99 days ($3*30.4375 \pm 7$ days)), the date of dose intake and the number of days since the last drug intake will be listed.

3.2.9. *Prior and concomitant medications and non-drug therapies*

Descriptive summary statistics will be provided by treatment group and overall on the safety population for ‘Prior and concomitant medications and non-drug therapies’.

Prior and concomitant medications:

Prior and concomitant medications will be coded using WHO-Drug Dictionary March 2013 version. The therapeutic class will correspond to the second level of Anatomic Therapeutic Class (ATC) code.

Listings containing prior and concomitant medications will be presented for the therapeutic class, preferred name and verbatim text, and will be sorted by country, centre, patient, chronological start date, therapeutic class, preferred name and verbatim text.

A frequency table of the number and percentage of patients will be provided for prior and concomitant medications only by therapeutic class and preferred name.

Prior and concomitant non-drug therapies and surgical procedures:

Prior and concomitant non-drug therapies will be coded using MedDRA version 16.0 and will be classified by Preferred Term (PT) and System Organ Class (SOC).

A concomitant therapy will be defined as a therapy started prior to baseline visit date and ongoing at baseline visit date, or started the day of baseline visit or after.

Listings containing prior and concomitant non-drug therapies will be presented for the SOC, PT and verbatim text, and will be sorted by country, centre, patient, chronological start date, SOC, PT and verbatim text.

A frequency table of the number and percentage of patients will be provided for prior and concomitant non-drug therapies only by SOC and PT.

An individual data listing containing concomitant surgical procedures will also be provided.

3.2.10. *Derived data*

The derived data are variables which are calculated from the raw data and not included in the database.

Age

Patient age (years) will be derived as $(\text{baseline visit date} - \text{birth date})/365.25$ and truncated to the largest integer that is less than or equal to the calculated result.

Time since the first histological diagnosis

Time since the first histological diagnosis (months) will be derived as $(\text{Date of screening visit} - \text{Date of first histological diagnosis} + 1) / 30.4375$ and truncated to the largest integer that is less than or equal to the calculated result.

Partial dates of histological diagnosis will be imputed to calculate times:

- If the day is missing and month is present, the 15 of the month will be used.
- If the day and month are missing, the 15 of June will be used.

Radical Prostatectomy Procedure

Time between screening visit and surgery (weeks) will be derived as $(\text{Screening Visit Date} - \text{Date of radical prostatectomy} + 1) / 7$.

Compliance

Time between first drug administration and RP (weeks) will be derived as $(\text{Date of first drug administration} - \text{Date of radical prostatectomy} + 1) / 7$.

Time between each drug intake (weeks) will be derived as $(\text{Date of drug intake at Visit } t - \text{Date of drug intake at visit } t-1 + 1) / 7$.

Partial dates of treatment will be imputed to calculate times:

- If the day is missing and month is present the 15 of the month will be used.
- If year is present and day and month are missing then the difference between years will be used.

Changes from baseline

Changes from baseline will be calculated as a difference from baseline (e.g. assessment at the visit – assessment at baseline).

Length of patient exposure in the study

Length of patient exposure in the study (months) will be calculated as [(Date of last visit attended – informed consent date) + 1] / 30.4375.

Duration of study drug exposure

Duration of study drug exposure (months) will be calculated as [(Date of last drug administration – Date of first drug administration) / 30.4375] + 3.

Adverse event

Time to onset of AE (days) = AE start date – date of randomisation.

Duration of AE (days) = (AE resolution date – AE start date) + 1.

Time-to-event criteria

BRFS (months) will be derived as (Date of first BR – date of randomisation + 1) / 30.4375.

EFS (months) will be derived as (Date of clinical disease progression or death from any cause – date of randomisation + 1) / 30.4375.

OS (months) will be derived as (Date of death from any cause – date of randomisation + 1) / 30.4375.

Disease specific mortality will be derived as (Date of death related to prostate cancer – date of randomisation + 1) / 30.4375.

PSADT (months) will be derived as (Date of sample when the first PSA value > than twice that of the first increased value – Date of sample of the first PSA value increased value (i.e. > 0.2 ng/mL) + 1) / 30.4375.

All of these time-to-event variables will be rounded to 1 decimal.

For BRFS, EFS, OS and Disease specific mortality, if the date of event or censor is prior to the date of randomisation, the data of event or censor taken into account will be the date of randomisation.

Rules for time-to-event data

The following table defines the rules for censoring data (for Kaplan-Meier analysis)

- BRFS

Event	Decision	Date of event or censor to consider for analysis
BR	Not censored	Date of BR (i.e. date of the first elevated PSA measurement is >0.2 ng/mL*)
No BR and no clinical disease progression and new hormonal treatment (ie triptorelin or similar)	Censored	Date of last evaluable sample before the start of new hormonal treatment
No BR and no clinical disease progression and no premature withdrawal from the study	Censored	Date of last evaluable sample assessment
No BR and no clinical disease progression and patient premature withdrawal from the study or lost to follow-up	Censored	Date of last evaluable sample before withdrawal from the study or last contact
Clinical disease progression before BR	Censored	Date of clinical disease progression
No BR but death	Censored	Date of last evaluable sample assessment

- BRFS – Sensitivity Analysis 1

Event	Decision	Date of event or censor to consider for analysis
BR	Not censored	Date of BR (i.e. date of the first elevated PSA measurement is >0.2 ng/mL*)
At least two consecutive visits missing before BR	Censored	Date of last visit preceding the missing consecutive visits
No BR and no clinical disease progression and new hormonal treatment (ie triptorelin or similar)	Censored	Date of last evaluable sample before the start of new hormonal treatment
No BR and no clinical disease progression and no premature withdrawal from the study	Censored	Date of last evaluable sample assessment
No BR and no clinical disease progression and patient premature withdrawal from the study or lost to follow-up	Censored	Date of last evaluable sample before withdrawal from the study or last contact
Clinical disease progression before BR	Censored	Date of clinical disease progression
No BR but death	Censored	Date of last evaluable sample assessment

- BRFS – Sensitivity 2

Event	Decision	Date of event or censor to consider for analysis
BR	Not censored	Date of BR (i.e. date of the first elevated PSA measurement is >0.2 ng/mL*)
Death (whatever the reason) without BR	Not censored	Date of death
No BR and no clinical disease progression and new hormonal treatment (ie triptorelin or similar)	Censored	Date of last evaluable sample before the start of new hormonal treatment
No BR and no clinical disease progression and no premature withdrawal from the study	Censored	Date of last evaluable sample assessment
No BR and no clinical disease progression and patient premature withdrawal from the study or lost to follow-up	Censored	Date of last evaluable sample before withdrawal from the study or last contact
Clinical disease progression before BR	Censored	Date of clinical disease progression

- EFS

